In this ongoing study we have examined pupil responses to phasic noxious heat stimuli to date in 19 normal volunteers and 4 subjects with migraine (but not in the presence of a headache). Studies were performed in a room with constant, low ambient light so that both constriction and dilation of the pupil could be observed. Pupil diameter was continuously monitored by an infrared camera (Eye-Trac™ system; Applied Science Laboratories) with the subject's chin resting on a chin rest and gaze on a fixed object presented on a monitor. A 4 cm² Peltier-controlled thermode was placed on the calf, with temperature maintained at 35°C and 5 sec stimuli at various temperatures applied every 30 sec. Subjects reported pain intensity with a visual analog scale (VAS) from 0 (no pain) to 100 (worst pain imaginable). Increasing probe temperature to 50°C resulted in pain report and pupil dilation, the former with a longer lag (Figure 2, typical response). As previously described with other stimuli (Chapman, 1999; Oka, 2007), there was a direct relationship between pupil dilation and noxious heat temperature as well as VAS pain intensity and unpleasantness.

We next examined the relationship between pupil response and pain report as a function of affective distress. We estimated affective distress as the sum of scores to the pain catastrophizing scale, the CSED depression scale, the state trait anxiety inventory, and the pain anxiety symptom scale and linearly regressed this on pain report. The residual from the regression line for each individual was related to baseline pupil diameter as a measure of tonic LC activity. Despite there being a very small range of affective distress in this largely normal population, the residual (tendency to adhere to cognitive-affective state in pain reporting) was significantly related to baseline pupil diameter (Figure 3).

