A more relevant drug to the question of chronic pain after surgery is gabapentin, and some clinical trials have suggested that perioperative treatment of this drug can reduce the incidence of this problem (Schmidt, 2013). In the NIH application we propose to test gabapentin rather than modafinil because our previous work with direct measures in rats and cerebrospinal fluid norepinephrine sampling in humans is consistent with gabapentin activating LC in both species (Hayashida, 2007). The pupil measurements in this feasibility study will more directly assess whether gabapentin does indeed increase LC activity in humans. Should it fail to demonstrate a reasonable effect size to dilate the pupil, we will revise the NIH application to study modafinil rather than gabapentin. As such, these preliminary data are very important to the design of the final study.

Study Design.

Hypotheses: (1) Gabapentin and modafinil will increase resting pupil diameter with a moderate effect size in patients with osteoarthritis; (2) Expectations will modify pain experience with a moderate effect size in these patients

Study design: Single-center, randomized, controlled study of gabapentin, modafinil, and placebo in 30 subjects (10 per group) with moderate osteoarthritis pain of the hip or knee or healthy individuals without pain

Primary outcome measures: (1) Resting pupil diameter and response to noxious stimuli after study drug; (2) Interaction between resting pupil diameter and correlation of cognitive-affective state to pain reporting.

Inclusion criteria: Adult, nonpregnant adults scheduled with moderate pain (verbal score of $\geq 4 \leq 7$ on 0-10 scale for average pain intensity with normal activity) from osteoarthritis of the knee or hip, or healthy individuals without pain, American Society of Anesthesiologists physical status 1-3, able and willing to perform the study procedures, including sitting in a chair for 45 min. Individuals must be able to read.

Exclusion criteria. (1) Inability to complete questionnaires; (2) Pregnancy; (3) Currently taking gabapentin or > 50 mg morphine equivalents/day; (4) advanced or unstable cardiac, pulmonary, renal or hepatic dysfunction; (5) history of previous eye surgery; (6) psychotic disorder or a recent psychiatric hospitalization.

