Data analysis. Pupil diameter data will be conditioned to remove blink and saccade artifacts and smoothed using an autoregressive filter. The local resting diameter will be determined representing the average smoothed value for the 500 msec preceding the stimulus onset. The pupil response to each stimulus is calculated as the mean pupil diameter during the 5 sec stimulus after accounting for lag time from onset of stimulus to onset of pupil response and is expressed as a % change from the local resting diameter (see our preliminary data for examples). Multidimensional Scaling (MDS) will be used to create a single dimensional scale from the catastrophizing and optimism scores (i.e., responses from these two questionnaires will be weighted and scaled to create a single-dimensional construct)

To determine the interaction among the factors of interest, and to accommodate the many repeated measures within each participant, we will utilize Generalized Estimating Equations. In our experience, the pupil response to painful stimuli is well modeled by a normal distribution with an identity link and an AR1 repeated measures covariance structure. To examine our hypotheses, we will model percent pupil change (the DV) using fixed effects for stimulus temperature, catastrophizing-optimism score (i.e., cognitive-affective state), and pre-stimulus baseline pupil diameter (i.e., LC activity). The association between cognitive-affective state and pain reporting will first be examined, and in a later block the moderating effect of baseline pupil size will be entered.

The goal of this feasibility study is to estimate the effect size of drugs on pupil diameter and the strength of interaction between pupil diameter and the relationship between cognitive-affective state.

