Expected results. We anticipate, based on preliminary data, that pain reporting will be weakly correlated with cognitive-affective state and that resting pupil diameter as a reporter of LC gain will interact with this correlation or tendency to apply cognitive style to pain reporting. We anticipate overall reduced pain reporting after placebo (placebo effect) and that the magnitude of this reduction and that of negative of pain will be inversely related to location on the optimism-catastrophizing continuum (i.e., greater placebo effect, greater effect of negative expectations of pain, and lesser effect of positive expectations of pain in strong optimists). After gabapentin or modafinil we anticipate that resting pupil diameter will be greater (i.e. greater tonic LC activity) than placebo. According to the gain concept, the effect of gabapentin on pain reporting across conditions should depend on cognitive-affective state, with overall reductions in pain reporting in strong optimists and amplification of pain in strong catastrophizers. The study is not powered to definitively show the effects of these drugs on either pupil diameter or its relationship to pain reporting as a function of optimism-catastrophizing. Rather, it is to provide feasibility, effect size, and variability data to support the choice of drug and power analysis for the eventual controlled study.

References

1. Alexander, JK, et al. Beta-adrenergic modulation of cognitive flexibility during stress. *J Cogn Neurosci* 2007;19:468-478.
2. Astafiev, SV, et al. Comment on "Modafinil shifts human locus coeruleus to low-tonic, high-phasic activity during functional MRI" and "Homeostatic sleep pressure and responses to sustained attention in the suprachiasmatic area". *Science* 2010;328:309-
3. Chapman, CR, et al. Phasic pupil dilation response to noxious stimulation in normal volunteers: relationship to brain evoked potentials and pain report. *Psychophysiology* 1999;36:44-52.
5. Geng, JJ, et al. A match made by modafinil: probability matching in choice decisions and spatial attention. *J Cogn Neurosci* 2013;25:657-669.
6. George, SA, et al. Altered locus coeruleus-norepinephrine function following single prolonged stress. *Eur J Neurosci* 2013;37:901-909.

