A Feasibility Study: Understanding and Altering Pain Expectations in Subjects With  
Osteoarthritis of the Knee or Hip  
Statistical Analyses Plan

NCT02155257

11/02/2018

To address the two primary hypotheses, linear mixed effects models will be employed. For each model, subject will be specified as a random effect to account for the repeated measures within individuals. To examine the impact of drug (i.e., placebo, gabapentin, modafanil) on tonic pupil diameter, pupil diameter will be regressed on fixed effects for drug, time (i.e., pre-drug vs post-drug), and a drug x time interaction. A group x time integration would be interpreted as evidence supporting the hypothesis that drug differentially impacted baseline pupil over time.

To examine the impact of tonic pupil diameter on the relationship between cognitive style (i.e., catastrophizing-optimism dimension) and pain reporting, VAS scores will be regressed on fixed effects for catastrophizing-optimism, tonic pupil diameter, and the interaction between catastrophizing-optimism x pupil diameter. A statistically significant interaction would be interpreted as evidence that tonic pupil diameter moderated the relationship between cognitive style and pain reporting. Where appropriate, all analyses are two-tailed with statistical significance interpreted at  $p < 0.05$ . The analyses will be conducted using R 3.4 and R Studio.

The sample size was based on estimating the feasibility of the protocol and on establishing effect size estimates. No formal statistical power calculations were conducted.

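### The SAP's pupil-moderation model does not state the level of tonic pupil or separate person-level from within-person differences, so its interaction may blend effects that cannot be told apart

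*SAP*

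**What the plan says.** The second paragraph of the SAP gives the moderation model. The pain score is regressed on catastrophizing-optimism, "tonic pupil diameter, and the interaction between catastrophizing-optimism x pupil diameter". For this and the other primary model, "subject will be specified as a random effect to account for the repeated measures within individuals". It names no person mean, no deviation from that mean, no random slope for pupil, and no time or drug term in this model. A significant interaction is to be read as moderation by tonic pupil. The SAP does not give the level at which tonic pupil enters.

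The protocol points to stimulus level. Under Data analysis, local resting diameter is the "average smoothed value for the 500 msec preceding the stimulus onset", and the protocol's own model uses "pre-stimulus baseline pupil diameter (i.e., LC activity") as a predictor.

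On the target, the documents point two ways:
- The preliminary data in the Background are between-person, with one residual per subject: "The residual from the regression line for each individual was related to baseline pupil diameter as a measure of tonic LC activity".
- Expected results predicts that the active drugs enlarge the resting pupil and that "the effect of gabapentin on pain reporting across conditions should depend on cognitive-affective state". That is a within-person, pre-to-post form of the same idea.
- Primary outcome 2 names no level: "Interaction between resting pupil diameter and correlation of cognitive-affective state to pain reporting".

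**The concern.** A pupil value taken before every stimulus varies in three ways: between people, between the pre-drug and post-drug sessions of one person, and from moment to moment. With a random intercept and one pupil coefficient, the model assumes that all three kinds of difference moderate the style-pain relation equally. If they do not, the fitted interaction is a precision-weighted average. Its weights depend on the number of stimuli and on how much the pupil fluctuates, and neither is a property of the hypothesis.

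Three things follow. A real between-person effect can be diluted almost to nothing. A significant result can come from within-person variation and be read as a statement about people. And if pupil-pain slopes differ between subjects, leaving out a random slope makes the standard error of the interaction too small.

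The study exists to supply effect sizes and variability for the later trial. A blended coefficient does not serve that purpose, because its weights would change with the next design.

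**Working it through.** **No plan figure to reproduce.** The SAP states that no power calculation was made. The sample of 30 is 3 groups of 10.

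**Inputs from the documents.** There are 30 subjects. The analysed pre-drug stimuli are 2 × 5 random plus 2 × 5 cued = 20. After drug, the random and cued paradigms are each given twice, which is 20 more if each has 5 stimuli (assumed), plus a miscue sequence of unstated length. That gives 40 stimuli without the miscue sequence, or about 45 if it also has 5.

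**Assumed inputs.** The documents give no variance for pupil or pain. Let *r* be the within-person pupil SD divided by the between-person pupil SD, and τ² the between-subject pain variance divided by the residual pain variance. Pupil is in between-person SD units, style in SD units and pain in residual SD units.

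**Weight of the within-person part.** In a random-intercept model, pooled interaction = w × within + (1 − w) × between, where

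w = m·r² / [m·r² + m/(1 + m·τ²)] = r² / [r² + 1/(1 + m·τ²)].

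With m = 40 and τ² = 1, the second term is 1/41 = 0.0244:

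| r | pupil ICC = 1/(1 + r²) | w |
|---|---|---|
| 0.1 | 0.99 | 0.010/0.0344 = 29% |
| 0.25 | 0.94 | 0.0625/0.0869 = 72% |
| 0.5 | 0.80 | 0.25/0.2744 = 91% |
| 1 | 0.50 | 1/1.0244 = 98% |

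The share passes 50% at r = √(1/41) = 0.16. If τ² also varies from 0.5 to 2, the range for r between 0.25 and 1 widens from 72–98% to 57–99%.

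**Effect on the estimate.** Take r = 0.5, a true between-person interaction of 0.5 and no within-person effect. The expected pooled value is 0.5 × (1 − 0.911) = 0.044. Simulation agrees: the pooled interaction averages about 0.04 and is significant in about 12% of trials. The person-level term averages about 0.50 and is significant in about 60%. At r = 0.1 the pooled estimate is about 0.33 with 47% rejection, against 59% for the person-level term.

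**Check on another scale** (m = 45, pain ICC 0.5, pupil scaled to total SD 1, true interaction 0.30 at one level only):

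| pupil ICC | between-only: pooled estimate, rejection | within-only: pooled estimate, rejection |
|---|---|---|
| 0.80 | 0.02, 10% | 0.29, 100% |
| 0.95 | 0.07, 17% | 0.23, 82% |
| 0.99 | 0.20, 40% | 0.12, 18% |

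**Missing random slope.** With no true interaction, r = 0.5, and pupil-pain slopes varying between subjects with SD 0.2, 0.4 or 0.6 (assumed), the pooled interaction rejects in about 10%, 21% and 35% of trials, against a nominal 5%. The inflation nearly vanishes when the pupil is very stable: 6% at a pupil ICC of 0.99 with slope SD 0.3 on the second scale.

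**Missing time term.** Expected results also predicts a fall in pain after placebo whose size depends on cognitive style. Assume such a style slope of 0.3 residual SD in all arms, and a pupil shift of 0.5 between-person SD in the two active arms. With no true moderation, the pooled interaction then rejects in 32% of trials at r = 0.5 and 82% at r = 0.1. The interaction with the pre-drug person mean rejects in about 5%.

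**The case against.** A reader might infer that the SAP definitely enters stimulus-level pupil, that its interaction mostly fails to test the individual-difference hypothesis, and that the within-person part is only drift. The documents do not support any of these as stated.

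- **Level.** The SAP is silent. The protocol's local resting diameter serves first as the denominator of the phasic response, and the protocol's model has pupil change, not pain, as its outcome. The SAP's other model treats pupil as pre- versus post-drug. With one value per session, w at equal pain variances would be 0.84, 0.54 or 0.19 for pupil ICCs of 0.80, 0.95 and 0.99. With one value per subject it would be 0. Stimulus level is the natural reading, but it is inferred.
- **Target.** Primary outcome 2 names no level, and Expected results predicts a drug-induced within-person effect. The within-person part is partly what the investigators want to know.
- **Size.** Whether the within-person part dominates depends on variances the documents do not give. At r = 0.1 it does not.
- **Stakes.** The protocol says the study is not powered for definitive conclusions. In the check at m = 45, the person-mean interaction has only 42–50% power for an effect of 0.30, even after the split.

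All of this limits the claim. It does not remove it: the plan commits to interpreting one interaction without saying what that interaction estimates, and a study meant to supply effect sizes depends on that more than on its p-value.

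**Conclusion.** The point holds in conditional form. The SAP leaves the level of tonic pupil undefined and has one undivided interaction. If pre-stimulus values are used, that interaction blends between-person and within-person effects, and a significant result cannot be assigned to either.

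The share of the within-person part runs from 29% to 98% over the assumed SD ratios of 0.1 to 1, with 40 trials and equal pain variances. At a ratio of 0.5 a between-person effect of 0.5 would be almost invisible. The understated standard error (10–35% type I error) requires slopes that vary between subjects and a pupil that moves appreciably within a person.

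Confidence is medium, because the level is inferred and every variance is assumed. The change is worth making all the same, since it settles the meaning of a primary analysis at almost no cost.

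**What to change.** In the SAP:

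1. State that tonic pupil is the pre-stimulus value.
2. Split it into three parts: the subject's pre-drug mean, the subject's pre-to-post change in mean (zero before drug), and the momentary deviation from the session mean.
3. Interact each part with catastrophizing-optimism.
4. Add time (pre/post) and its interaction with catastrophizing-optimism, so that a style-dependent placebo response is not read as pupil moderation.
5. Add a random slope for the momentary deviation.
6. State in advance which interaction tests primary outcome 2. The pre-drug between-person term matches the preliminary result. The pre-to-post term addresses the drug prediction and should be reported separately, as should the momentary term.
7. Report all three interactions with confidence intervals.

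The cost is SAP wording, a few derived variables, a few more fixed effects and one more random effect. Data collection does not change. The between-person estimate rests on 30 subjects and stays imprecise: in the check above, its empirical SD was about 0.17–0.18 for a true value of 0.30. The split buys a clear estimand, not a decisive test.
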